6.2.2 Local control rate

1) Purpose

To explore the efficacy of protocol treatment for unresectable advanced or recurrent gastric cancer, determine the local control rate of the best overall response, which is SD or better, confirmed by Day 180.

2) Analysis items

Local control rate (disease control rate of irradiated target lesions).

3) Analysis methods

- (1) Construct a waterfall plot for the local control rate.
- (2) Summarize the responses of irradiated target lesions in a contingency table, and calculate the cumulative disease control rate and the Clopper & Pearson two-side 90% confidence interval.

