Although there is no established consensus on the efficacy (additive or synergistic effect) of the combination of radiotherapy and immunotherapy, its efficacy has been reported in many basic studies, translational studies, case reports, and relatively small clinical studies in recent years. We have also reported the induction of cancer antigen-specific T lymphocytes after irradiation in patients with esophageal squamous cell carcinoma (2) and the drug-resistant/unresectable recurrent gastric cancer showing an abscopal effect in combination with immuno-cell therapy (3). The mechanism is thought that irradiation-induced cell death of cancer cells became new antigen and a tumor immune response was activated *in vivo*.

Significance of this examination

This clinical trial is designed to evaluate the additive effect to nivolumab and radiotherapy in patients

with unresectable advanced or recurrent gastric cancer who have been diagnosed to have an inadequate response (intolerance or progression: PD) to standard (first- and second-line) chemotherapy by combining radiation therapy immediately before the third-line nivolumab treatment. The trial will be positioned as a proof of concept (POC) to explore the efficacy of this therapy by conducting exploratory clinical and immunological analyses as a phase I/II study. The safety of this combination therapy will also be investigated as a secondary study. It is positioned to provide basic data on median survival time (MST) and percentage of local control for future randomized controlled trials (RCTs) of this therapy.

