2.6. Evaluation items

The primary endpoint of this clinical trial is the disease control rate of non-irradiated target lesions, in order to explore the efficacy (additive effect) of radiotherapy to immunotherapy with nivolumab, which is already established as third-line chemotherapy in unresectable advanced or recurrent gastric cancer. Secondary endpoints will also include 1) median survival time (MST) and 2) safety (grade and frequency of adverse events), 3) local control rate (disease control rate of irradiated target lesions), and 4) immunological parameters.

(1) Primary endpoint

Disease control rate

The rate of patients with a best overall response of stable disease (SD) or better confirmed by 180 days, starting from the start date of radiotherapy (Day 1). CT (MRI is also acceptable) and whole-body PET-CT will be used to determine overall response such as complete response (CR), partial response (PR), SD, progressive disease (PD) at each imaging time according to the RECIST Guidelines Version 1.1. If imaging is not available, the patient is considered deficient (NE). CR or PR as the best overall response is defined as two or more consecutive CRs or PRs. If the best overall response does not meet the criteria for CR or PR, and the patient has no PD on the 6th dose of nivolumab and Day 120, the best overall response is considered to be SD. For evaluation, target lesions other than those treated with local radiotherapy are considered as target lesions. If the lesions cannot be evaluated based on the above criteria, they will not be included in the analysis for best overall response.

(2) Secondary endpoint

1) Median survival time (MST)

Overall survival is defined as the period from the start date of radiotherapy until the date of death from any cause. In surviving cases, the last date of confirmation of survival is the date of termination (survival confirmed by telephone contact is acceptable, but confirmation of survival should be recorded in the medical record). Untraceable cases are terminated on the last date of confirmed survival before the loss of follow-up. At the end of the study period, all enrolled cases will be confirmed alive.

2) Safety (grade and frequency of adverse events)

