The frequency of adverse events occurring from the start date of radiotherapy to the end of study will be tabulated by adverse event name and worst grade according to CTCAE ver.4.0. All adverse events are summarized without regard to causal relationships to the study treatment. A serious adverse event is defined as having occurred if at least one of the following adverse events is observed, and the frequency and proportion of serious adverse events is calculated.

- ① Death during protocol treatment or within 30 days of last protocol treatment.
- ② Death with undeniable causal relationship to protocol treatment after 31 days of last protocol treatment.
- ③ Grade 4 infection with neutropenia.
- ④ Grade 4 non-hematological toxicity (excluding adverse events in the blood/bone marrow).

3) Local control rate

The rate of patients with a best overall response of SD or better confirmed by 180 days, starting from the start date of radiotherapy (Day 1). CT (MRI is also acceptable) and whole-body PET-CT will be used to determine overall response such as complete response (CR), partial response (PR), SD, progressive disease (PD) at each imaging time according to the RECIST Guidelines Version 1.1. If imaging is not available, the patient is considered deficient (NE). CR or PR as the best overall response is defined as two or more consecutive CRs or PRs. If the best overall response does not meet the criteria for CR or PR, and the patient has no PD on the 6th dose of nivolumab and Day 120, the best overall response is considered to be SD. For evaluation, target lesions are tumors that are treated with local radiotherapy. If the lesions cannot be evaluated based on the above criteria, they will not be included in the analysis for best overall response.

4) Immunological parameters

Histological examination

- Analysis of the tumor microenvironment by immunohistochemistry.
 - * Immunohistochemistry will be performed in cases with available biopsy and/or resected surgical specimens.

Peripheral blood test

- Analysis of peripheral blood lymphocyte subset
- Measurement of cytokines in plasma
- Analysis of regulatory T cell and antigen-specific T cell function

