2.8. Expected number of cases

40 cases.

Basis for setting

Based on a previous study (ONO-4538-12 study) (5), the disease control rate is set at 40%. At a one-side significance level of 5% and a power of 80%, a sample size of 39 cases are required to detect an additional 20% improvement expected from the study treatment.

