2.10. Statistical analysis

(1) Statistical analysis of the evaluation

The composition of the population to be analyzed shall be as follows:

- 1) All enrolled cases: the population of enrolled patients, excluding duplicate enrollments and incorrect enrollments.
- 2) All eligible cases: the population excluding ineligible cases (posterior ineligibility, ineligibility at enrollment, offending enrollment) from all enrolled cases.
- 3) Largest analyzed population (FAS): all eligible cases for whom treatment was administered.

(2) Method of analysis

Primary endpoints

- 1) Disease control rate

For FAS cases, summarize the responses of non-irradiated target lesions in a contingency table, and calculate the cumulative disease control rate and the Clopper & Pearson two-side 90% confidence interval. The disease control rate was defined as the total number of patients with CR/PR/SD divided by the number of eligible patients.

Secondary endpoint

- 1) MST

For FAS cases, estimate the MST using the Kaplan-Meier method, along with a two-sided 95% confidence interval using the Brookmeyer-Crowley method.

- 2) Safety

For all enrolled cases, data regarding AEs and toxicities were tabulated, and the Clopper & Pearson two-sided 95% CI was calculated.

- 3) Local control rate

For FAS cases, summarize the responses of irradiated target lesions in a contingency table, and calculate the cumulative disease control rate and the Clopper & Pearson two-side 90% confidence interval. The disease control rate was defined as the total number of patients with CR/PR/SD divided by the number of eligible patients.

- 4) Immunological parameters

Analyzes are performed at Fukushima Medical University Hospital, Kanagawa Cancer Centre,

and by outsourced testing, as appropriate.

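### Local control is scored with the systemic stable-disease rule, so a stable irradiated lesion in a patient who dies or stops imaging before Day 120 is either counted as not controlled or dropped, and the plan does not say which

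*SAP*

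**What the plan says.** Protocol 2.6 defines local control by repeating the primary endpoint's definition and changing one thing: the target lesion is now the irradiated tumour. The measure is best overall response by RECIST 1.1 up to Day 180. A complete or partial response needs two consecutive assessments. Failing that, stable disease is credited if "the patient has no PD on the 6th dose of nivolumab and Day 120, the best overall response is considered to be SD". A patient without imaging is not evaluable, and lesions that cannot be evaluated are left out of the analysis.

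Protocol 2.10 defines the rate as the "total number of patients with CR/PR/SD divided by the number of eligible patients". SAP 6.2.2 tells the analyst to "Summarize the responses of irradiated target lesions in a contingency table, and calculate the cumulative disease control rate" with a two-sided 90% Clopper-Pearson interval. It names no divisor and says nothing about death or missing scans. SAP 6.5 plans no sensitivity analysis for missing values.

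Protocol 1.1 gives the figure a use: the trial is to supply median survival and the "percentage of local control for future randomized controlled trials (RCTs) of this therapy".

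**The concern.** Local control should describe what happens to the irradiated lesion. The rule also requires that the patient be assessed free of progression at the sixth dose and at Day 120. A patient who dies at Day 100 with an irradiated lesion that never grew has no in-field failure, yet cannot be scored as stable. What happens next depends on which section the analyst follows.

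This will not be rare. Eligibility (Protocol 3.1) asks for an expected survival of at least 3 months, which is shorter than 120 days. The sixth dose falls on Day 85 to 92 if no dose is delayed (first dose Day 15 to 22, plus 70 days), so stable disease needs about four to five further weeks of follow-up.

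The level at which progression is judged is also unclear. The stable-disease sentence speaks of the patient, and Protocol 2.7 records progression from imaging and clinical findings together. The target-lesion sentence in Protocol 2.6 and the wording of SAP 6.2.2 point instead to the irradiated lesion.

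At stake is a planning figure for a later trial that could move with early death and loss of imaging as well as with in-field control.

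**Working it through.** **The plan's own figures.** The documents give no assumed or target local control rate, so there is none to reproduce. The sample size in Protocol 2.8 concerns systemic disease control (40% against 60%, one-sided 5%, power 80%). An arcsine calculation gives 38.1, hence the stated 39, but this does not bear on local control. The illustrations below rest on assumptions.

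**The two rules on the same data.** Assume 40 eligible, treated patients and 4 true in-field failures. Let g be the number of patients with a stable irradiated lesion who die or leave imaging before Day 120.

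- Protocol 2.10, eligible patients as divisor: (40 − 4 − g)/40
- Protocol 2.6, not evaluable excluded: (40 − 4 − g)/(40 − g)
- Lesion scored at its last assessment: (40 − 4)/40 = 36/40 = 90.0% (90% CI 78.6 to 96.5) for every g

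| g | Protocol 2.10 (90% CI) | Protocol 2.6 exclusion (90% CI) | Gap, points |
|---|---|---|---|
| 8 | 28/40 = 70.0% (56.0 to 81.7) | 28/32 = 87.5% (73.6 to 95.6) | 17.5 |
| 12 | 24/40 = 60.0% (45.8 to 73.1) | 24/28 = 85.7% (70.2 to 95.0) | 25.7 |
| 16 | 20/40 = 50.0% (36.1 to 63.9) | 20/24 = 83.3% (65.8 to 94.1) | 33.3 |

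**Deaths alone.** Protocol 1.1 cites median survival of about 6 to 13 months, a background figure not specific to third-line treatment. Assuming exponential survival, the share dead by Day 120 is d = 1 − 2^(−120/(30.4375 × m)), with m the median in months.

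- m = 13: d = 0.190, about 8 of 40
- m = 6: d = 0.366, about 15 of 40

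Assume further that 30% of irradiated lesions have a confirmed response before any exit, 60% are stable and 10% progress in-field with this recorded, and that death is unrelated to lesion status.

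- Protocol 2.10: 0.30 + 0.60 × (1 − d) = 78.6% (m = 13) to 68.0% (m = 6)
- Protocol 2.6 exclusion: 0.786/(0.786 + 0.10) = 88.7% to 0.680/(0.680 + 0.10) = 87.2%
- Never progressing in-field: 90%

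Here the stable lesions lost number 24 × d, about 5 to 9 of 40. The upper part of the 8 to 16 range therefore needs loss of imaging beyond death.

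**Level of progression.** If progression is read at patient level, the planning rates of 40% to 60% systemic control leave up to 24 to 16 of 40 patients who could count as locally controlled only through a confirmed response of the irradiated lesion. If it is read at lesion level, this loss does not arise while imaging continues.

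**The case against.** The other side has several sound points.

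- Two consecutive response assessments secure local success without any Day 120 condition. They can come from the third-dose and sixth-dose scans (about Day 43 to 50 and Day 85 to 92, each ±14 days). Only stable lesions and unconfirmed responses are exposed.
- A reader might infer that progression elsewhere automatically becomes a local failure. The documents do not establish that. The irradiated tumour is the target lesion, the Day 120 and Day 180 scans are dated from the start of radiotherapy, a scan is scheduled at cessation of treatment, and Protocol 2.4 can allow observation to continue after growth elsewhere. On the lesion-level reading, out-of-field progression matters only where it ends imaging.
- The exclusion rule alone stays fairly close to 90% in both illustrations.
- SAP 6.2.2 plans a waterfall plot, SAP 6.7 an analysis by administration status, and SAP 8.7 a listing of diameters over time. The endpoint is secondary and untested.
- Censoring at the last scan may itself be informative.

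These points narrow the concern without removing it. The plots and listings do not say how an early death is scored, the two divisors still conflict, and the level of progression is still unstated. The point about censoring is a reason for a sensitivity analysis.

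**Conclusion.** The point holds in a limited form. Under the stated rules, a patient with a stable or unconfirmed-response irradiated lesion who dies or stops imaging before Day 120 is a non-success under Protocol 2.10 and is excluded under Protocol 2.6. SAP 6.2.2 does not settle this. With 8 to 16 such patients in 40, the two rules differ by 17.5 to 33.3 points. With deaths alone, at 19% to 37% by Day 120, the Protocol 2.10 rule gives about 79% to 68% against 90%. All of these sizes depend on the assumed lesion outcomes and survival, which the documents do not give.

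Two further inferences should be resisted. One is that no simple proportion could work: scoring each lesion at its last assessment gives 36/40 whatever the number of early exits. The other is that the planned 40% to 60% systemic control rate shows how many patients will be imaged at both time points, so that the reported rate would largely reflect survival. Patients with systemic progression can still be scanned, so that rate is not the share imaged.

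The primary analysis is unaffected. The change is worth making because Protocol 1.1 offers this figure for planning later trials.

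**What to change.** In Protocol 2.6 and 2.10 and SAP 6.2.2:

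1. Define progression for local control on the irradiated lesion alone.
2. Reconcile the exclusion in Protocol 2.6 with the divisor in Protocol 2.10, and state one divisor in the SAP.
3. Add the cumulative incidence of in-field progression from Day 1 (Aalen-Johansen) at Day 120 and Day 180 with 95% confidence intervals. Use all scans, treat death without in-field progression as the competing event, and censor patients no longer imaged at their last scan.
4. State whether a death after imaging has stopped is a competing event or is censored.
5. Give scoring at the last lesion assessment as a sensitivity analysis, because censoring after out-of-field progression may be informative.
6. Keep the table of CR, PR and SD as a supportive summary.

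The cost is wording, one further estimate and one sensitivity analysis. SAP 8.7 already lists irradiation site, examination dates with tumour diameters, and date of death or last verified survival, so no new visits or patients are needed. The downside is the censoring assumption, which item 5 puts in view.

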6.3 Interim analysis

Not conducted in this study.

6.4 Adjustment analysis by patient background and baseline

Not conducted in this study.

6.5 Sensitivity analysis (handling of omissions or missing values)

Not conducted in this study.

6.6 Examination of homogeneity between institutions

Not conducted in this study.

6.7 Subgroup and supplementary analyses

The disease control rate and local control rate are analyzed in the same manner as in the main analysis by irradiation site and administration status, etc.

Survival is analyzed in the same manner as the main analysis by completion of study treatment and by irradiation site, etc.

7. Safety considerations

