2.1. Schema

- Patients with unresectable advanced or recurrent gastric cancer.
- Patients who are diagnosed as ineffective (intolerant or progression) to standard treatment (first-line or second-line chemotherapy) and have two or more lesions that can be confirmed by imaging.
- 40 cases

Obtaining consent to participate in the trial, checking eligibility criteria, enrolment

Treatment = radiotherapy ➤ Nivolumab (anti-PD-1 Ab)

Radiotherapy: 4.5 Gy once daily for 5 days (total 22.5 Gy/5 times/5 days) to the lesion thought to be the main cause of symptoms if there are symptoms such as pain or paralysis, or to the largest lesion if asymptomatic (second largest lesion if radiotherapy to the largest lesion is difficult). The day that radiotherapy is started is Day 1.

Nivolumab: Dosing is started between Days 15 and 22; Nivolumab is administered at 3 mg/kg (body weight) or 240 mg every 2 weeks for a total of six doses.

End of administration

Follow-up (~Day 180 ± 14) and efficacy assessment (Day 180 ± 14)

End of trial

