2.2. Research design

Phase I/II, single-arm, open (non-randomized), prospective study

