2.5. Criteria for changes in dosage/use

1) Radiation dose escalation and dose reductions will not be performed. Nivolumab dosage and administration should be in accordance with the recommendations for the treatment of unresectable advanced or recurrent gastric cancer (Appendix).

2) Criteria for discontinuation of treatment

- ① Nivolumab (anti-PD-1 Ab) discontinuation criteria:
 - 1) Failure to meet the criteria for initiation of nivolumab (anti-PD-1 Ab) in '2.3.(2) Nivolumab (anti-PD-1 Ab) treatment' and failure to resume treatment within 14 days of the planned treatment date.
 - 2) If a patient requests discontinuation of nivolumab treatment, irrespective of whether or not it is associated with an adverse event.
 - 3) Death during protocol treatment.
 - 4) Ineligibility due to a known protocol violation, change of pathology diagnosis after enrolment, etc.
 - 5) It is deemed inappropriate to continue treatment due to apparent worsening of clinical symptoms caused by disease progression.
 - 6) Occurrence of Grade 2 or higher interstitial lung disease.
 - 7) Occurrence of Grade 2 or higher eye disorders.
 - 8) Occurrence of Grade 3 or higher bronchospasm, diarrhea, colitis, neurotoxicity, hypersensitivity reactions and injection reactions.
 - 9) Occurrence of Grade 3 or higher thrombocytopenia.
 - 10) Abnormalities in liver function that fulfill one of the following criteria have emerged. AST or ALT $> 5-10$ times the upper limit of the facility reference value for more than 2 weeks.

AST or ALT > 10 times the upper limit of the facility reference value. Total bilirubin levels > 5 times the upper limit of the institutional reference value. Concurrent AST or ALT > 3 times the upper limit of the facility reference value and total bilirubin > 2 times the upper limit of the facility reference value.

11) The principal investigator or a member of research team decides that continued treatment with nivolumab is not appropriate.

② Criteria for discontinuation of radiotherapy

Discontinue radiotherapy if any of the following occur:

- 1) Failure to meet the treatment criteria for radiotherapy in '2.3(2) – Radiotherapy'.
- 2) When the attending doctor decides that discontinuation is necessary due to an adverse event.
- 3) If the patient requests discontinuation of radiotherapy, irrespective of whether or not it is associated with an adverse event.
- 4) Patient deaths.

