6.2. Response to the occurrence of serious adverse events

If an adverse event as defined in the preceding paragraph is deemed to be serious, it meets one of the following criteria:

- ① Resulting in Death,
- ② Life-threatening,
- ③ Requiring inpatient hospitalization or prolongation of existing hospitalization for treatment,
- ④ Resulting in permanent or conspicuous disability or dysfunction,
- ⑤ Causing congenital anomalies in offspring.

However, hospital admissions stipulated in the research protocol, hospital admissions solely for the purpose of carrying out a therapy or examination planned before the research (before consent was obtained) and during the study (e.g. planned surgery or examinations), and hospital admissions other than for the purpose of therapy or examinations associated with an adverse event (e.g. medical examination) are not treated as serious. In addition, evaluations related to progression of the primary disease or efficacy of treatment are not handled with adverse events.

Attending doctor manage serious adverse events in accordance with the 'Procedures for handling illnesses, etc.'. In addition, attending doctor report serious adverse events to the Adverse Event Information Desk of Ono Pharmaceutical Industries, Ltd. within 72 hours of receiving the information.

7. Criteria for discontinuation and completion

- 1) In this study, completion of protocol treatment is defined as completion of six doses of nivolumab (anti-PD-1 Ab) followed by 22.5 Gy/5 doses/5 days of radiotherapy. Study completion is also defined as the end of observation at 6 months (Day180) after the start of treatment. Survival will, however, be confirmed at the end of the study period.
- 2) Discontinuation of treatment in individual cases is in accordance with '2.5. Criteria for changes of dosage/use'.
- 3) Discontinuation of the trial is decided by the chief investigator at each institution.
- 4) The principal investigator will monitor opinions and information from the nivolumab manufacturer and distributor, academic information such as papers, and regulatory information from PMDA and other sources, and will always manage the appropriateness of continuing this study.

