6.2 Investigation of secondary endpoints

6.2.1 Median survival time

1) Purpose

To explore the efficacy of protocol treatment for unresectable advanced or recurrent gastric cancer, determine the median survival time using overall survival defined as the period from the start date of radiotherapy until the date of death from any cause.

2) Analysis items

Survival time from the start date of study treatment to death from any cause.

3) Analysis methods

- (1) Estimate and draw the survival function using the Kaplan-Meier method with log-rank test.
- (2) Estimate of the median survival time is calculated using the Kaplan-Meier method, along with a two-sided 95% confidence interval using the Brookmeyer-Crowley method.
- (3) Estimate of the probability survival rate is calculated using the Kaplan-Meier method, along with a two-sided 95% confidence interval using the Greenwood's formula.

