8.6 List of treatment status

1) **Purpose**

Prepare a list of treatment status for cases subjected to safety analysis.

2) **Analysis object**

Safety analysis population.

3) **Analysis items**

Case number, age, gender, radiotherapy start date, radiotherapy end date, nivolumab administration date, concomitant medications.

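### SAP 6.7 compares survival by treatment completion from Day 1, although completers must live to about Day 85-92, so the split is biased in their favour

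*SAP*

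**What the plan says.** SAP 6.7: "Survival is analyzed in the same manner as the main analysis by completion of study treatment and by irradiation site, etc". The main survival analysis, in SAP 6.2.1, counts time from the start of radiotherapy and instructs: "Estimate and draw the survival function using the Kaplan-Meier method with log-rank test". It is run in the FAS (SAP 3.1 and 3.2), which takes every eligible patient who was treated and sets no minimum survival.

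Protocol section 7 says that "completion of protocol treatment is defined as completion of six doses of nivolumab", together with the five-fraction radiotherapy course. For nivolumab, "Dosing is started between Days 15 and 22" (Protocol 2.1), with two-week intervals up to the sixth dose. Under Protocol 2.5 nivolumab stops on death, on "apparent worsening of clinical symptoms caused by disease progression", and where a missed dosing condition is followed by "failure to resume treatment within 14 days of the planned treatment date".

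The design is a "Phase I/II, single-arm, open (non-randomized), prospective study" (Protocol 2.2). The SAP gives no landmark, no time-dependent covariate and no caution on interpretation. SAP 6.4 and 6.5 rule out adjusted and sensitivity analyses.

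**The concern.** Patients are grouped by something that happens about three months after the survival clock starts. Completers cannot die before their sixth dose, whereas every death before that point is assigned to the non-completers. The curves therefore separate even when completion does nothing.

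With one arm, the log-rank test in SAP 6.2.1 has groups to compare only in splits such as those in SAP 6.7, so this is one of the few places where it would yield a p-value. Protocol 1.1 intends the survival data to inform later randomised trials, and an apparent survival gain from finishing treatment could mislead that planning. The split by irradiation site in the same SAP sentence does not have this fault, because the site is chosen before Day 1.

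**Working it through.** The documents state no power, stopping rate or expected result for this split, so there is no planned figure to reproduce.

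**1. Day of the sixth dose** (Protocol 2.1)

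- First dose on Day 15-22; six doses give five 14-day intervals, and 5 × 14 = 70 days.
- Earliest 15 + 70 = Day 85. From the latest permitted start, 22 + 70 = Day 92.
- Protocol 2.5 lets a dose resume within 14 days of its planned date, so the sixth can fall later. If all five intervals slipped by 14 days and each slip moved the later doses, it would fall on Day 155-162.

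**2. Effect on the medians when completion does nothing**

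Assume constant hazard with median *m* months, a sixth dose on average 87.5 days after Day 1, and 30.44 days per month. The range for *m* is the 6-13 months in Protocol 1.1, a general chemotherapy figure used only to set a range.

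- Share dead before the sixth dose = 1 − 2^(−87.5 / (30.44 *m*)). For *m* = 6: 1 − 2^(−0.479) = 28%.
- Completers' median = *m* + 87.5/30.44 = *m* + 2.9 months.
- The non-completers' median below adds an assumed 25% stopping unrelated to survival.

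| True median (months) | Dead before sixth dose | Completers' median | Non-completers' median |
|---|---|---|---|
| 6 | 28% | 8.9 | 2.3 |
| 9 | 20% | 11.9 | 3.0 |
| 13 | 14% | 15.9 | 6.4 |

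**3. False rejection by the log-rank test from Day 1**

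Simulated trials of n = 40 with no completion effect and a nominal 5% test. Assumptions:

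- First nivolumab uniform on Day 15-22, sixth dose 70 days later.
- 20% or 40% stopping unrelated to survival; a completer is alive at the sixth dose and has not stopped.
- Censoring uniform on 365-1279 days, from the accrual and study periods in Protocol 2.11.
- In the delay settings, each of doses 2-6 has a 15% chance of slipping 1-14 days.
- 3,000 trials per setting with constant hazard, 1,500 with no deaths before Day 60; simulation error at most about 1.3 points.

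The Day 60 setting is there because Protocol 3.1 asks for expected survival of at least 3 months.

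| Setting | Stopping | m = 6 | m = 9 | m = 13 |
|---|---|---|---|---|
| Constant hazard, on schedule | 20% | 82% | 65% | 50% |
| | 40% | 51% | 34% | 24% |
| Constant hazard, delays | 20% | 84% | 68% | 53% |
| | 40% | 54% | 35% | 25% |
| No deaths before Day 60, delays | 20% | 54% | 34% | 22% |
| | 40% | 25% | 15% | 10% |

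At least 94% of these rejections favour completers. A separate constant-hazard simulation with medians of 4-13 months and 10-40% stopping gave 24-99%.

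**4. Choice of landmark**

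- Day 120 leaves 120 − 92 = 28 to 120 − 85 = 35 days for total dose delay.
- With delays, a Day 92 landmark would class about 8-14 of 40 eventual completers as non-completers; Day 120 misplaces about 0.1 or fewer per trial.
- The test from Day 120 rejects in 5-8% of trials in every setting.
- Non-completers still alive at Day 120, constant hazard: for *m* = 6 and 20% stopping, 40 × 0.20 × 2^(−119/182.6) = 8 × 0.637 = 5.1; for *m* = 13, 8 × 0.812 = 6.5. With 40% stopping these double to 10.2 and 13.0. With no deaths before Day 60 the upper ends are about 7 and 14.

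**The case against.** The mechanism is hard to dispute, so the case on the other side concerns weight.

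- **Direction.** A bias towards completers does not fix the result of one trial. In the mildest setting only about 71-73% of null trials lean that way, where 50% would mean no bias. This stands: the claim is about bias, not a guaranteed result.
- **Size.** The stopping rates, the slip probability and the Day 60 floor have no source in the documents, and the 6-13 month range does not describe third-line nivolumab after radiotherapy. This stands too. The entry criterion on expected survival also makes the Day 60 figures a fairer guide than constant hazard from Day 1.
- **The test.** SAP 6.7 names no test or significance level. Carrying the log-rank test over is a reading of the reference to the main analysis, though a natural one. Without a p-value, the curves and medians would still be biased.
- **Importance.** The analysis is supplementary in an exploratory trial, and SAP 5.2 and 8.7 would make early deaths and stopping reasons visible. Visibility does not correct the comparison.
- **Definition.** The SAP does not define completion of study treatment; equating it with Protocol section 7 is an inference. That section also requires the radiotherapy course, although a patient given a sixth dose will in practice have finished it.
- **Simpler remedy.** One could drop the p-value, label the split descriptive and state the problem. That is a tolerable minimum, but it still publishes two medians distorted by construction.

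**Conclusion.** The concern holds. Followed as written, SAP 6.7 gives a comparison biased towards completers, and nothing elsewhere in the documents corrects it. The Day 85-92 guarantee and the direction of the bias come from the documents' own schedule and definitions.

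The size is conditional. Depending on assumed survival, stopping and delay, the nominal 5% test rejects in 10% to 84% of null trials in the main settings, so even the mildest doubles the nominal rate. The damage is confined to this supplementary split. It should be corrected before analysis, but it does not threaten the trial's main conclusions.

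**What to change.** In SAP 6.7, replace the Day 1 comparison by completion with wording such as:

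> Survival by completion is a Day 120 landmark analysis. It includes FAS patients alive and in follow-up at Day 120, classified by whether protocol treatment as defined in Protocol section 7 (radiotherapy course and sixth nivolumab dose) was completed by that day. Survival is measured from Day 120. The result is descriptive, because stopping for progression or toxicity is related to prognosis. The number of patients completing after Day 120 is reported.

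Day 120 is already an imaging time (Protocol 2.7), but the reason for choosing it is the room it leaves for delayed doses. A Cox model with completion as a time-dependent covariate is an alternative.

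The same section also splits disease control by administration status, which the SAP does not define. Define it; if it means doses received or completion, label that split descriptive as well.

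**Cost.** SAP text and a few lines of code. No new data are needed: SAP 8.6 already lists "radiotherapy start date, radiotherapy end date, nivolumab administration date", and SAP 8.7 lists survival dates. Patients who die before Day 120 leave this comparison. About 5-7 non-completers of 40 remain with 20% unrelated stopping, or 10-14 with 40%, so power is low. Confounding by progression and toxicity remains under either method.
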